When target sample size is reached, the study statistician (who will not be involved in the conduct of the study) will unblind the treatment allocation (identify who is in group A vs B but not identify the groups themselves as active drug or placebo) and estimate the treatment effect between the two groups based on the primary outcome (intention-to-treat). If there is a statistically significant treatment effect ($p<0.05$), the study statistician will do the following statistical analyses. For the primary outcome we will compare the proportion of randomized patients that responded at day 14 of therapy in the placebo arm compared with the treatment arm using a two sample test for proportions. We will perform intent-to-treat analysis according to the treatment arm subjects were randomized to. We will also perform a per-protocol analysis based on subjects who completed the 7 days of prednisone or placebo as per protocol. The same analysis will be performed for the proportion responding to therapy at 1 month. Logistic regression analysis will then be performed to adjust for potential confounders, such as age, gender, *Pseudomonas aeruginosa* or methicillin-resistant *Staphylococcus aureus* (MRSA) infection and lower FEV₁, as these factors have been associated with failure to recover lung function after an exacerbation (3, 25). For the additional secondary outcomes, absolute change in pulmonary function tests, length of hospitalizations and change in sputum measurements,

we will use parametric (t-test), or non-parametric (Mann-Whitney) two sample comparison test. Linear regression analysis will be then performed to adjust for potential confounders, as listed above. Time to subsequent exacerbation will be compared using a Cox proportional hazard model. Potential confounders will be adjusted for in the Cox-proportional hazard model. All secondary outcomes will be analyzed both as intention-to-treat and per-protocol. All outcomes will be obtained for all subjects irrespective of whether they completed the study per protocol. In the case of missing data, we will perform the analysis on complete (complete case analysis). To determine whether diabetic patients have a different response compared to non-diabetic patients, we will perform a sensitivity analysis comparing return to baseline lung function in diabetics vs non-diabetics according to treatment group.

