If when the statistician estimates the treatment effect between the two groups (above), there is NOT a statistically significant treatment effect ($p>0.05$), the statistician will re-calculate the sample size based on the observed data from 84 participants, in order to determine what sample size is required to observe a statistically significant effect. This data will be provided to the DSMB who will decide whether or not to continue the study, based on feasibility and the clinical relevance of the treatment effect size. Appendix 1.1 includes detailed plans for the analysis of the extension study, which will be designed as an adaptive trial (52).

H. Potential Challenges and Alternative Approaches

The main challenge of this study is the large estimated treatment effect size. The future adaptive trial design, however, allows us the flexibility to calculate the necessary sample size based on observed data if the difference between groups is clinically but not statistically significant. These data will inform the decision whether to continue the trial with the addition of other centers in either Canada or the United States (Deliverables and Future Directions). Another challenge is the number of potential confounders influencing lung function recovery. We have designed this trial to be pragmatic, that is, reflective of real life conditions, as it is not possible to stratify based on all the variables that could affect response such as concomitant medications, hospital vs home IV therapy, choice and duration of antibiotic therapy. Therefore, we will collect all this information and sensitivity analyses will be done to determine whether these variables affect the results.

I. Personnel Requirements and Study Timeline:

We will require a research coordinator at each site over the study period (see Budget).

J. Knowledge Translation (KT):

We have developed a KT plan with the assistance of [name], scientific director of KT at the Hospital for Sick Children (Appendix). Our target audiences for the results of this study are CF clinicians, patients and researchers. We will partner with CF Canada to implement the following KT strategies for disseminating our results: publishing in an open-access journal for all audiences, presenting at national (Canadian Clinics conference) and international CF

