Appendix 1.1

Adaptive Study Design

We propose to complete the current study as planned until the target sample size is reached. Statistician [name] will then unblind the treatment allocation (identify who is in group A vs B but not identify the groups themselves as active drug or placebo) and analyze the data to determine whether a significant treatment effect was observed. If the p value is significant ($p<0.05$) [name] will complete the analysis as outlined in the Statistical analyses section.

If the p value is not significant ($p>0.05$), [name] will re-calculate the sample size based on the observed data from 84 participants, in order to determine what sample size is required to observe a statistically significant effect. This data will be provided to the DSMB who will decide whether or not to continue the study, based on feasibility and the clinical relevance of the treatment effect size. If the DSMB decides it is feasible and the treatment effect is clinically relevant, the study will be continued until the new re-calculated sample size is reached and all study site investigators and personnel will remain blinded to treatment allocation. Additional study sites may be added and further funding may be sought for the extension study. The data collected as part of this current study will be used in the extension study. The extension study will be designed as an adaptive trial (52). Adaptive trial designs are study designs that allow for adaptations to be made to the trial after its initiation without undermining the validity and integrity of the results (53). They are increasingly being used to study rare diseases in which there are limited numbers of subjects and trial durations are frequently very long. The significance level (i.e. p value) of the extension study will be adapted to adjust for the fact that unblinded analysis was conducted at the end of this current study(54).

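### Section G calls for the per-protocol, 1-month, adjusted and secondary analyses when the primary test is significant, and names none of them for a null, stopped or extended trial

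*Combined protocol and SAP*

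**What the plan says.** Section G (Statistical analyses) has the study statistician estimate the primary intention-to-treat effect once the target sample size is reached. The text then splits in two.

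**Significant branch.** "If there is a statistically significant treatment effect" at p<0.05, "the study statistician will do the following statistical analyses". What follows is the rest of the analysis plan:

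- the two-sample test of proportions at day 14;
- a per-protocol analysis: "We will also perform a per-protocol analysis based on subjects who completed the 7 days of prednisone or placebo as per protocol";
- 1-month recovery: "The same analysis will be performed for the proportion responding to therapy at 1 month";
- adjusted models: "Logistic regression analysis will then be performed to adjust for potential confounders", with linear regression for continuous outcomes;
- two-sample tests for lung function change, length of stay and sputum markers, and a Cox model for time to the next exacerbation;
- a general rule: "All secondary outcomes will be analyzed both as intention-to-treat and per-protocol";
- the comparison of diabetic with non-diabetic patients.

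**Non-significant branch.** If p>0.05, "the statistician will re-calculate the sample size based on the observed data from 84 participants" and passes the result to the DSMB, which decides whether the trial goes on. No other analysis is named.

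Appendix 1.1 (Adaptive Study Design) repeats both branches. On a significant result the statistician "will complete the analysis as outlined in the Statistical analyses section". On a non-significant result the steps are re-calculation and the DSMB decision. If the trial is extended, the appendix says that the data already collected are re-used and that the significance level is adjusted. It does not mention the secondary, per-protocol or adjusted analyses.

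**The concern.** The analyses that help a reader interpret the primary result are attached to only one of its possible outcomes. If the primary test is null and the DSMB stops the trial, Section G has no further analysis to carry out. Anything run afterwards would be chosen by people who already know the primary result.

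A null result would matter here. The Background says that oral steroids are already used in CF exacerbations and that the trial is meant to inform practice. Appendix 1.2 rates the risk as moderate because of prednisone's known side effects. After a null day 14 result, readers would want the 1-month recovery, lung function change, biomarker, per-protocol and adjusted estimates with their confidence intervals.

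**Working it through.** **Step 1. Set the branches side by side.**

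| Situation at 84 patients | Section G | Appendix 1.1 | Section E |
|---|---|---|---|
| p<0.05 | Full list | Full list, by reference to Section G | Some comparisons described, no condition |
| p>0.05, DSMB stops | Primary estimate and new sample size only | Same | Same unconditional wording |
| p>0.05, DSMB extends | Refers to Appendix 1.1 | Data re-used, significance level adjusted; list not mentioned | Same unconditional wording |

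The Section E wording without a condition covers length of stay, duration of IV antibiotics and time to the next exacerbation. It does not cover the per-protocol or adjusted analyses. Nowhere do the documents say that the list is run whatever the primary p-value.

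**Step 2. Reproduce the plan's sample size.** Inputs from Section F: 30% response on placebo, 60% on prednisone, 5% significance, 80% power. Section F does not state sidedness; two-sided is assumed.

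n per arm = [z(0.975)·√(2·p̄·(1−p̄)) + z(0.80)·√(p1(1−p1)+p2(1−p2))]² / (p2−p1)², with p̄ = (0.30+0.60)/2 = 0.45.

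- 1.960·√(2·0.45·0.55) = 1.960·0.7036 = 1.379
- 0.842·√(0.21+0.24) = 0.842·0.6708 = 0.565
- (1.379+0.565)² / 0.30² = 3.78/0.09 ≈ 42

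This gives 42 per arm, 84 in total, as stated. The other Table 3 rows also reproduce (163, 93 and 61 per arm). A one-sided test would give 33 and a continuity correction 49, so a two-sided, uncorrected test is the one that matches.

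**Step 3. Chance of entering the p>0.05 branch.** With 42 per arm:

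power ≈ Φ{[(p2−p1)·√42 − 1.960·√(2·p̄·(1−p̄))] / √(p1(1−p1)+p2(1−p2))}

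Example at 30% v 45%: (0.15·6.481 − 1.960·0.6847)/0.6764 = (0.972−1.342)/0.6764 = −0.547. Φ(−0.547) = 0.292, so the chance of a non-significant result is 1 − 0.292 = 71%.

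The exact column adds up the binomial probabilities of all pairs of response counts for which the pooled z-test is not significant.

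| True prednisone rate (placebo 30%) | Source of the rate | Formula | Exact |
|---|---|---|---|
| 60% | Design assumption | 20% | 17% |
| 55% | Table 3 | 36% | 32% |
| 50% | Table 3 | 54% | 51% |
| 45% | Table 3 | 71% | 69% |
| 40% | Assumed scenario | 84% | 83% |
| 30% | No effect | 95% | 95% |

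**Step 4. What these percentages mean.** They are the chance of a non-significant primary test, and not the chance that the list is never run:

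P(list never run) = P(p>0.05) × P(trial stopped, or extended with the list omitted, given p>0.05)

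The documents give no value for the second factor, which can lie anywhere from 0 to 1. Each percentage is therefore an upper bound.

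**The case against.** The strongest reply is that Section G describes an order of work. The first item on the conditional list is the primary test itself, which must already have been done to obtain the p-value. The same paragraph holds the missing-data rule and the commitment to obtain outcomes for all subjects, neither of which can sensibly depend on significance. The text says if, and never only if. On this reading the plan means: finish the analysis if significant; otherwise settle the extension question first. If the trial is extended, holding back secondary comparisons until the end is good practice.

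Much of this stands. A reader might infer that the plan withholds results from a null trial. The documents do not say so. They are silent on what is analysed after a stop, Section E promises some comparisons outright, Section H promises sensitivity analyses on concomitant treatment and care setting, and the dissemination plan does not depend on the result. Adverse events go to the ethics boards and the DSMB in either case, and Appendix 1.2 has a midpoint safety analysis.

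A reader might also infer that the condition inflates the reported primary effect. It does not: the primary difference is estimated in both branches, and removing the condition would leave that estimate unchanged.

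A defence that the condition is a hierarchical multiplicity procedure has no support in the text. Such a procedure would limit confirmatory claims; it would not remove the need to estimate and report.

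The reply does not fill the null branch. Neither Section G nor Appendix 1.1 says what is analysed when the trial stops, or that the list is run when an extension ends.

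**Conclusion.** The point holds as a defect in the stated analysis rule and as a conflict with Section E. Followed literally, Section G and Appendix 1.1 call for the per-protocol, 1-month, adjusted and secondary-outcome analyses after p<0.05. They call for none of them after p>0.05, whether the trial stops or is extended.

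The p>0.05 branch is not remote. Its chance is 17-20% even if the design assumption of 30% v 60% is right, 69-71% at Table 3's 30% v 45%, and 95% with no effect. Section H itself names the large assumed effect as the main challenge. These figures assume 42 evaluable patients per arm, a 30% placebo rate and a two-sided 5% test, and they are upper bounds on the list never being run.

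The documents do not support a claim of planned selective reporting. The sample size, the primary estimate and adverse event reporting to the ethics boards and the DSMB are unaffected.

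**What to change.** Remove the condition in Section G and Appendix 1.1, and bring Section E into line. State that:

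- all pre-specified primary, secondary, per-protocol, adjusted and safety analyses are done and reported, with estimates and confidence intervals, at the final analysis, whatever the primary p-value;
- the final analysis takes place at 84 patients if the primary result is significant or the trial is stopped, and otherwise at the end of the extension;
- if the trial is extended, secondary comparisons on the first 84 patients are held back until the extension ends;
- the p-value at 84 serves only as an input to the decision to continue or stop the trial.

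The change should be made before the allocation is unblinded at 84. It costs a wording change in the two places and a little more analysis work if the primary result is null. Sample size, data collection and conduct do not change.

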1. Role of pulmonary exacerbations in CF- In the natural history of CF, there is a progressive decline in lung function with episodes of acute worsening of respiratory symptoms, called pulmonary exacerbations (PExs). PExs occur quite frequently in CF patients. In 2007, 38% of all CF patients seen in care centers in the US were treated with IV antibiotics for at least one PEx (2). Although there is no generally accepted definition of PEx, clinical features include increased cough or sputum, fever, weight loss, absenteeism from school or work due to illness, tachypnea, new crackles, decreased exercise tolerance, decreased pulmonary function tests or reduced oxyhemoglobin saturation, or a new finding on chest radiograph (14). The requirement for hospitalization or IV antibiotics is often used to determine the severity of a PEx (15-16). PExs requiring IV antibiotics have been associated with decreased lung function in children (17-18), with CF-related diabetes (19), sleep disturbances (20) and health-related quality of life (21). PExs have long term effects as well. In a large epidemiologic study using the Toronto CF database, we showed that over half of the decline in forced expiratory volume in 1 second (FEV₁) over the lifetime of an individual with CF is directly attributable to these episodes of exacerbation (6). In addition, investigators, including ourselves, have identified that a quarter to a third of CF patients do not regain >90% of baseline FEV₁ and only approximately 40% recover full lung function following an exacerbation (3-5). The average time from initiation of antibiotic treatment for a PEx to the highest observed FEV₁ has been shown to be 8.7 days with a median of 10 days (SD 4.0 days) (22). Regaining lung function following a PEx is key as low FEV₁ is one of the most significant predictors of mortality in CF. Using data from the Cystic Fibrosis Foundation Patient Registry, Liou et al. developed a multivariable logistic regression model to identify key clinical features of CF that determined 5-year survivorship (23). Annual number of acute PExs was identified as a characteristic of the disease that predicted survival. Several investigators have examined the reasons for failing to recover lung function after treatment of PEx. Female gender, worse nutritional status and greater drop in FEV₁ from baseline to exacerbation have all been identified as risk factors for failing to recover lung function, but none of these factors are actually modifiable at the time of treatment of the exacerbation (3, 24). Studies that have investigated mechanisms by which these failures may occur have focused on serum markers of inflammation (eg CRP and WBC), measured either at the beginning or the end of antibiotic therapy, and shown that higher levels are associated with

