Research coordinators will approach all patients at day 0 of intravenous antibiotic treatment for a pulmonary exacerbation to obtain consent, determine eligibility and to complete a Data Collection Form. If the participant is female and post-menarchal, a pregnancy test will be done at day 7 before randomization to prednisone or placebo. If the test is positive, the participant is ineligible for randomization. If the test is positive, the participant and her primary care CF physician will be informed of the result in private. Every effort will be made to keep any pregnancy test results private.

All study sites will perform pulmonary function tests at day 7 of IV antibiotic therapy for a pulmonary exacerbation as part of clinical care. If based on day 7 pulmonary function testing (± 2 days), a patient has not recovered $>90\%$ of their baseline FEV_1 % predicted (Non-Responders), they will be randomized into the placebo or prednisone treatment arm (**Figure 2 Randomization Flow Chart**). Baseline lung function will be defined as the best FEV_1 in the 6 months prior to the PEx (or in the 12 months prior to PEx if there are no measurements in the 6 months prior) (3). Patients who achieve $>90\%$ of their baseline FEV_1 % predicted at day 7 (Responders) will not be randomized to prednisone or placebo but will continue in the study as outlined below.

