pulmonary function data points were available (n=228), we determined that 50% of patients will recover >90% of their baseline FEV₁ at day 7 of antibiotic treatment, with the remaining 50% available for randomization to either prednisone or placebo treatment. Of the 50% who do not recover >90% of baseline FEV₁ at day 7, 30% of these will go on to recover FEV₁ at day 14 of antibiotic treatment. We therefore estimated a 30% placebo response rate. Using these estimates, we calculated the sample size (**power two proportions** command in Stata 13.1) for the comparison of two proportions (Table 3).

For this study, we are aiming for a clinically significant treatment effect size of approximately two and a half-fold (30% response in the placebo arm vs 60% in the treatment arm). In order to have 80% power (at a significance level of 5%) we would need a sample size of **84 (42/arm)**. Estimating a 50% participation rate and a 20% drop out rate, we will need to approach 210 patients.

Since 50% of all patients who present with a PEx recover their lung function by day 7 of antibiotic therapy, 30% of patients will not experience more than a 10% relative drop in FEV₁ (inclusion criteria) and 10% of CF patients have diabetes and are on insulin which is an exclusion criteria (CPDR 2012 and personal communication-CF clinic directors), we will need to screen approximately 650 exacerbation events to approach 210 patients and enroll 105 patients into the study (Table 3). Over the 3 year study period, we expect to enroll enough study participants from all study sites) which will give us a sufficient population from which to enroll our necessary study sample size. We have had face to face meetings and discussions with our team of co-investigators who have been involved in the design and are fully committed to participating in this study. We have successfully collaborated with this team of researchers in previous clinical trials (10, 51) and fully expect we will achieve our current stated aims.

G. Statistical analyses

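### The primary day-14 recovery test makes no use of day-7 FEV₁, a pre-treatment value held for every randomised patient; the cost is a modest loss of efficiency if that value is prognostic

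*Combined protocol and SAP*

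**What the plan says.** Section D (Study protocol) has all sites measure lung function at day 7 of IV antibiotics. Its allocation rule opens "If based on day 7 pulmonary function testing" and sends to randomisation those who have not regained more than 90% of baseline FEV₁ % predicted. Section E sets the primary outcome as the same 90% threshold at day 14.

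Section G says that, at the target size, the statistician will "estimate the treatment effect between the two groups based on the primary outcome (intention-to-treat"). If p<0.05, "the study statistician will do the following statistical analyses". The list that follows contains the primary comparison of proportions "in the placebo arm compared with the treatment arm using a two sample test for proportions" and then a logistic regression for potential confounders. Those are introduced as examples: age, gender, two infections and low FEV₁ ("infection and lower FEV₁, as these factors have been associated with failure to recover lung function after an exacerbation"). FEV₁ has no time point or scale there. If p>0.05, Section G and Appendix 1.1 call for sample-size re-calculation and a DSMB decision on extension.

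For the lung-function changes, Section G plans two-sample tests followed by linear regression. Section E(ii) does not say from which time point change is measured. Section F plans on 30% versus 60% recovery.

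**The concern.** The randomised patients are those at or below 90% of baseline on day 7, and the endpoint asks whether they are above 90% on day 14. A patient at 89% and a patient at 60% may well differ in their chance of crossing that line, yet the primary test treats them alike. Section C requires a relative FEV₁ drop of 10%, and the randomisation paragraph mentions blocking but no stratification on day-7 FEV₁, so the design does not remove this variation either.

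The value is already collected, and it exists for everyone randomised. Adjusting for it therefore loses no one further under the complete-case rule.

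One p-value decides whether the trial ends at 84 patients or goes to re-calculation and possible extension, so extra precision has a use there. Tying the adjusted analysis to a significant first result leaves it out in the case where the DSMB most needs a precise estimate.

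**Working it through.** **1. The plan's own figure.** Inputs from Section F: 30% and 60%, 80% power, 5% level. Two-sided is inferred, because the two-sided uncorrected formula gives 42 (one-sided gives 33). With pooled proportion 0.45:

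n = [1.96·√(2·0.45·0.55) + 0.8416·√(0.3·0.7 + 0.6·0.4)]² / 0.30² = 41.97, so 42 per arm and 84 in total. This reproduces.

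Exact power of the uncorrected z test at 42 per arm is 82.8% (30% v 60%), 67.9% (30% v 55%) and 49.4% (30% v 50%). Its exact size is 5.1% at a common rate of 30% and 6.2% at 45%.

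**2. A range for prognostic strength.** The documents give no correlation. Section F does say that "50% of patients will recover >90% of their baseline FEV₁ at day 7 of antibiotic treatment". For the other half it gives the day-14 rate, 30%: "Of the 50% who do not recover >90% of baseline FEV₁ at day 7, 30% of these will go on to recover FEV₁". Day-7 non-responders who recover are therefore 0.5 × 0.30 = 15% of all exacerbations, and overall day-14 recovery cannot exceed 50% + 15% = 65%.

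Assume overall day-14 recovery of 45, 50, 55 or 60%, that is, 60, 70, 80 or 90% of day-7 responders still recovered (for example 0.5 × 0.6 + 0.15 = 0.45). Assume also that day-7 and day-14 values are bivariate normal, with day 7 cut at its median. Solving P(not recovered day 7, recovered day 14) = 0.15 gives r = 0.458, 0.588, 0.713 or 0.836.

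Among randomised patients only, r′ = r·√(1 − 2/π) / √(1 − 2r²/π). For r = 0.713 this is 0.713 × 0.603 / 0.822 = 0.52. The four values are 0.30, 0.40, 0.52 and 0.68.

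**3. Power with adjustment.** Simulation used 20,000 runs per setting, day-7 values truncated at the threshold and marginal recovery rates held at the stated values. The model was logistic regression on arm and day-7 value. The risk difference was standardised over all 84 patients, with an influence-function SE times √(84/81), and tested at 1.96.

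| r′ | 30 v 60, unadjusted (same runs) | 30 v 60, adjusted | Difference | 30 v 55, adjusted | 30 v 50, adjusted |
|---|---|---|---|---|---|
| 0 | 82.4 | 81.0 | −1.4 | 66.2 | 48.7 |
| 0.30 | 82.4 | 82.7 | +0.3 | 68.5 | 49.5 |
| 0.40 | 82.9 | 84.4 | +1.5 | 69.9 | 51.7 |
| 0.52 | 83.4 | 87.4 | +4.0 | 73.5 | 54.3 |
| 0.68 | 83.0 | 91.4 | +8.4 | 78.3 | 59.7 |

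Variance falls by about 4, 8, 14 or 25% at the four non-zero correlations. That is equivalent to 84/0.96, 84/0.92, 84/0.86 or 84/0.75, or about 87.5, 91, 98 or 112 unadjusted patients.

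A skewed day-7 distribution gave 82.9, 83.3, 85.5 and 88.8% at 30% v 60%. A separate simulation, indexed by the AUC of day-7 FEV₁ for recovery, gave no gain at AUC 0.63, about 4 points at 0.74 and about 8 at 0.82.

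**4. Size.** The adjusted test rejected in 5.4 to 5.8% of runs at a 30% null and 5.5 to 5.9% at 45%. The smaller AUC-based simulation gave 4.6 to 5.7%. Held to a true 5% at the 30% null, adjusted power at 30% v 60% is about 80, 81, 83, 86 and 90% for r′ from 0 to 0.68, against about 83% unadjusted. A repeat with other random numbers came out about a point higher.

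**5. Lung-function change.** The variance of ANCOVA relative to change from day 7 is (1 − r²)/(1 + k² − 2rk), with k = day-7 SD / later SD. At k = 1 and r = 0.5, 0.7, 0.9 the ratios are 0.75/1.0, 0.51/0.6 and 0.19/0.2, so variance is 25, 15 or 5% lower. At k = 0.8 the reductions are 11, 2 and 5%; at k = 1.25 they are 43, 37 and 39%.

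**The case against.** The best defence is that nothing in the primary test is broken. It is valid under randomisation, it matches the sample-size method, and it reaches the planned power. That stands.

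The gain rests on an assumed correlation, and this stands too. Section F does not say whether the 228 exacerbations behind its rates met the trial's 10% drop criterion. Section B names a "greater drop in FEV₁ from baseline to exacerbation have all been identified as risk factors for failing to recover lung function", but that concerns the fall at presentation among all exacerbations, not day-7 FEV₁ among patients already selected as day-7 non-responders. Part of the gain also reflects a slightly liberal test. Against that, the unadjusted test is itself at 6.2% when the common rate is 45%, and a gain remains at the two highest correlations.

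Linear regression of FEV₁ change on arm and starting FEV₁ gives the same arm effect as ANCOVA, so for FEV₁ part of the secondary proposal is already planned. The covariate is not defined, however, and FVC and FEF₂₅₋₇₅ have no matching day-7 term.

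Two stronger readings are tempting.

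- A reader might infer that the 84-patient decision has no test, because the comparison of proportions is listed after it. The decision is tied to the primary outcome by intention to treat, Section G gives one test for that outcome, and Section F sizes the trial on it. The intended test is readily inferred, and a sentence of clarification is enough.
- A reader might take the recovery rates in Section B (two-thirds to three-quarters regaining more than 90% of baseline, and 75% responding) as evidence of strong prognosis. Both exceed the 65% ceiling implied by Section F, so they cannot be placed in this model and support no part of its range.

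**Conclusion.** The point holds as lost efficiency and a poorly placed adjusted analysis. It does not show bias or under-powering, and the stated 84 is right for its assumptions.

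At 30% v 60% the gain is about 0 to 4 points for within-randomised correlations of 0.30 to 0.52, and about 8 at 0.68. There is a loss of about 1 to 2 points if day-7 FEV₁ carries no information. With size held at 5%, the advantage at low correlations disappears. At 30% v 50%, most of the power shortfall remains whatever the adjustment. All of this assumes bivariate normality and an overall day-14 recovery rate that the documents do not give.

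The dependence of the adjusted analysis on a significant first result needs no such assumption. As worded, a non-significant trial has no planned adjusted estimate. The missing time point and scale for the FEV₁ covariate is a minor gap.

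**What to change.** Before unblinding:

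- Specify the primary intention-to-treat analysis as logistic regression of day-14 recovery on arm and continuous day-7 FEV₁ (% of baseline). Report the standardised risk difference with a robust SE, and take the CI and the two-sided 5% test from that SE. This keeps the effect on the scale of Section F's planning rates.
- Use this one test for the 84-patient p<0.05 decision, and carry it into the re-calculation and extension in Section G and Appendix 1.1.
- Keep the two-sample test of proportions as supportive, and as the fallback if the model does not converge.
- Run the adjusted analysis whatever the first p-value.
- For FEV₁, FVC and FEF₂₅₋₇₅ at day 14 and 1 month, use ANCOVA on arm and the same measure's day-7 value.
- As minor clarifications, state that the 84-patient decision uses the named primary test, and give the time point and scale of the FEV₁ covariate.

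No new data or visits are needed. The work is SAP wording, plus making the re-calculation and the extension's significance level consistent with the adjusted test, which takes more than a sentence. The statistical price is the possible 1 to 2 points of power and a size of about 5.4 to 5.9%, against 5.1 to 6.2% for the unadjusted test.
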